4.1 Planned Sample Size

A Simon's two-stage Minimax design (Simon, 1989) was used to calculate sample size for Cohort 1. Cohort 1 will have a minimum of 14 subjects and a maximum of 33 subjects, with the maximum occurring if and only if at least 4 subjects have an objective response in the first stage of the trial. The alternative admissible 2-stage design (Jung et al., 2004) was used to calculate sample size for Cohort 2. Cohort 2 will have a minimum of 13 subjects and a maximum of 35 subjects, with the maximum occurring if and only if at least 3 subjects have an objective response in the first stage of the trial. The total minimum sample size for the trial is 27, with a maximum of 68 subjects.

The design for Cohort 1, platinum ineligible subjects, is based on a prior published ORR of 23% for atezolizumab monotherapy (Balar et al., 2017). The null hypothesis that the true ORR is 0.23 will be tested against a one-sided alternative. The null hypothesis will be rejected if 13 or more responses are observed in 33 subjects. This design yields an actual 1-sided type I error rate of 0.0244 and power of 0.7027 when the true ORR is 0.43 for the combination.

The design for Cohort 2, platinum refractory subjects who are anti-PD-L1 naïve, is based on a prior published ORR of 15% for atezolizumab monotherapy (Rosenberg et al., 2016). The null hypothesis that the true ORR is 0.15 will be tested against a one-sided alternative. The null hypothesis will be rejected if 10 or more responses are observed in 35 subjects. This design yields an actual 1-sided type I error rate of 0.0249 and power of 0.7092 when the true ORR is 0.33 for the combination.

Based on simulations with the two-stage, two-cohort design, the overall type-1 error rate will be approximately 4.7%, and the power for the trial, indicating at least one of the two cohorts will be positive given the alternative hypotheses are true, is approximately 91%.

4.2 Analysis Populations

For the purpose of statistical analysis, there will be 2 analysis populations: Full Analysis Set (FAS) and the Efficacy Evaluable (EE) Set.

The FAS consists of all subjects taking any amount of trial vaccine, whether MVA-BN-CV301 or FPV-CV301. The FAS will be the primary population for all analyses.

The EE Set consists of all subjects from the FAS who meet the following criteria:

- Received 2 prime doses of MVA-BN-CV301 (Weeks 1 and 4)
- Have a baseline CT/MRI scan assessable per RECIST v1.1

The EE set will be used for sensitivity analyses of the primary and secondary efficacy endpoints.

Although the primary efficacy analysis is on the FAS population, enrollment may continue for Stage 1 until the EE set reaches the full sample size of 14 for Cohort 1, or 13 for Cohort 2 ([Section 2.6.4](#)).

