## 4 Trial Design

### 4.1 Experimental Design

This is a Phase 2, single-arm, multi-institutional clinical trial designed to study the combination of CV301 with atezolizumab in the first-line treatment of UC not eligible for cisplatin-containing chemotherapy (Cohort 1) and in the second-line treatment of UC previously treated with standard first-line cisplatin-based chemotherapy (Cohort 2). The trial will be performed using an optimal two-stage design within each cohort ([Simon, 1989](#)). For the purpose of this trial, subjects are considered enrolled once they have received their first dose of trial product.

Stage 1, Cohort 1: Enroll 14 subjects. If objective response is not achieved in at least four subjects, the cohort will be stopped for futility. If objective response is achieved in at least four subjects, the cohort will proceed to Stage 2.

Stage 1, Cohort 2: Enroll 13 subjects. If objective response is not achieved in at least three subjects, the cohort will be stopped for futility. If objective response is achieved in at least three subjects, the cohort will proceed to Stage 2.

Stage 2, Cohort 1: Enroll an additional 19 subjects, such that a total of 33 subjects are available for the primary endpoint analysis.

Stage 2, Cohort 2: Enroll an additional 22 subjects, such that a total of 35 subjects are available for the primary endpoint analysis.

Further details of the two-stage design are in [Section 9](#).

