### **Rationale**

To be conservative, and to include all treated subjects for the final analysis, the FAS is now used as the primary population for all analyses, including efficacy. The EE population has been modified to be more inclusive such that a larger proportion of the population may be used for the sensitivity analyses, as well as determination of Stage 1 success.

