Trial medication refers to dosing with atezolizumab.

Treated Subjects

A subject is considered treated once they have received the first dose of trial product.

Trial Day (Study Day)

The day of trial is defined from the day of first vaccination. The day of first vaccination is defined as Day 1, the day after first vaccination is Day 2, and so on. Similarly, the day before first vaccination in the screening period is defined as Day -1, and so on. Note, no reference is made to the time of the vaccination in the calculation of the trial day, i.e., at midnight a new trial day begins regardless of the time of first vaccination. Note, to maintain conformance with Clinical Data Interchange Standards Consortium (CDISC) data standards, in datasets “trial day” will be referred to as “study day.”

Baseline

If not otherwise specified, “baseline” refers to the last measurement prior to first treatment with vaccine, including re-screening or pre-treatment unscheduled visit values. Note for determination of baseline values, data that are collected on the day of first vaccination but prior to the first vaccination, per protocol, will be considered pre-treatment data and will be eligible to be used as baseline values. Baseline data will be summarized without specification as to which visit the data were originally reported.

In cases where no pre-treatment values exist for a baseline parameter within a subject, the subject will be considered as having no baseline, and post-baseline changes and percent changes will not be able to be calculated.

Screening Phase

All data collected from the initial screening visit (within 28 days prior to first dose) until first dose of trial vaccine. This may include any unscheduled or re-screening visit results up to the first trial vaccination.

Active Trial Phase

All data collected at the visit of first vaccination (Visit 1) through Visit 14 plus 30 days, including unscheduled visits, will be considered part of the active trial phase. For safety analyses, data will be collected until 30 days (Visit 14 for completers) after the last treatment. For subjects who discontinue treatment early, the 30 days will start at the most recently received trial product.

Long Term Follow-up (LTFU) Period

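### The Full Analysis Set requires vaccine while enrolled, treated and TEAE start at any trial product, so a subject given only atezolizumab would be missing from every AE, exposure and ORR summary

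*SAP*

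**What the plan says.** Protocol 9.3 and SAP 4.2 define the FAS in the same words: "The FAS consists of all subjects taking any amount of trial vaccine, whether MVA-BN-CV301 or FPV-CV301". SAP 4.2 adds that "The FAS will be the primary population for all analyses" and that "there will be 2 analysis populations: Full Analysis Set (FAS) and the Efficacy Evaluable (EE) Set". The second set lies inside the first: "The EE Set consists of all subjects from the FAS who meet the following criteria". Protocol 9.9 bases the safety evaluation on the FAS, and protocol 9.9.3 and SAP 4.4.7.10 do the same for exposure. No separate safety set is defined.

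Other definitions use a wider starting point. In protocol 4.1, "subjects are considered enrolled once they have received their first dose of trial product". In the SAP General Definitions, "A subject is considered treated once they have received the first dose of trial product". Protocol section 8 defines trial product as CV301 and atezolizumab together, and the SAP lists atezolizumab among the trial products. A TEAE begins at or after the first trial product (protocol 9.9.1; SAP General Definitions), and PFS and OS run from first treatment.

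A third group of definitions goes back to vaccine. In the SAP, baseline "refers to the last measurement prior to first treatment with vaccine", and both Trial Day and the end of the Screening Phase are set by the first vaccination.

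**The concern.** Both products are scheduled at Visit 1 (protocol 4.2.2.2) and neither document says which is given first. If the infusion came first and the subject had a reaction or withdrew before any injection, that subject would be enrolled and treated, and the reaction would be a TEAE by definition. The subject would still be outside the FAS, and therefore outside the EE Set.

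Safety is the main issue. Protocol 2.8.1 describes this trial as the first to study CV301 with atezolizumab, and its cohorts may stop at 14 or 13 subjects. A Day 1 event in a treated subject could be missing from both numerator and denominator of every AE table. The exclusion would also depend on something that happened after treatment began, which an all-treated set is meant to avoid. For ORR, a subject who stops that early is unlikely to respond, so leaving the subject out most likely raises the estimate.

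**Working it through.** **1. The plan's own design figures.** Inputs are from SAP 4.1. Cohort 1: n1 = 14, continue if responses exceed r1 = 3, n = 33, success at r = 13, null 0.23, alternative 0.43. Cohort 2: n1 = 13, r1 = 2, n = 35, r = 10, null 0.15, alternative 0.33. The exact two-stage calculation is

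P(success | p) = Σ over x from r1+1 to n1 of b(x; n1, p) × P(X2 ≥ r − x), with X2 ~ Bin(n − n1, p).

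- Cohort 1: type I error 0.02437, power 0.70266 (stated 0.0244 and 0.7027).
- Cohort 2: type I error 0.02494, power 0.70918 (stated 0.0249 and 0.7092).

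All four figures reproduce.

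**2. Following one atezolizumab-only subject through the definitions.**

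| Item | Requires or starts at | Source | Subject included? |
|---|---|---|---|
| Enrolled | any trial product | Protocol 4.1, SAP 2.1 | Yes |
| Treated | any trial product | SAP General Definitions | Yes |
| TEAE | any trial product | Protocol 9.9.1, SAP General Definitions | Yes, by definition |
| Disposition table | screened and treated | SAP 4.4.7.1 | Yes |
| Subject-level listings, including AEs | all eCRF data | SAP 4.4.1, 4.4.8.1 | Yes |
| FAS | vaccine | Protocol 9.3, SAP 4.2 | No |
| EE Set | FAS and two prime doses | SAP 4.2 | No |
| AE summaries | FAS | Protocol 9.9, SAP 4.4.8.1 | No |
| Exposure summaries | FAS | Protocol 9.9.3, SAP 4.4.7.10 | No |
| ORR | FAS | Protocol 9.7.1, SAP 4.4.5.1 | No |
| Trial Day | first vaccination | SAP General Definitions | Undefined |

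**3. Size if one such subject occurs.** The documents give no expected number, so one is an assumption; zero is possible.

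- Share of a Stage 1 cohort: 1/14 = 7.1% (Cohort 1), 1/13 = 7.7% (Cohort 2).
- Cohort 1 at the success threshold, one non-responder outside a full FAS of 33: 13/33 = 39.4% on the FAS, 13/34 = 38.2% on all treated.
- Cohort 2 likewise: 10/35 = 28.6% and 10/36 = 27.8%.

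**4. What it costs to include the subject.** Suppose one certain non-responder is counted within the 33 (or 35), with the other subjects responding at the design rates and the thresholds unchanged. A Stage 2 subject replaces n by n − 1 in the formula; a Stage 1 subject replaces both n1 and n by one less.

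| | Type I error | Power |
|---|---|---|
| Cohort 1, design | 0.0244 | 0.703 |
| Cohort 1, one in Stage 2 | 0.0189 | 0.657 |
| Cohort 1, one in Stage 1 | 0.0182 | 0.644 |
| Cohort 2, design | 0.0249 | 0.709 |
| Cohort 2, one in Stage 2 | 0.0209 | 0.681 |
| Cohort 2, one in Stage 1 | 0.0197 | 0.657 |

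Inclusion is conservative: both type I error and power fall.

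**The case against.** The strongest reply is that the case may never arise. Both products are due at one visit, administration details are in a pharmacy manual that was not supplied (protocol 6.6), and a subject who receives any vaccine later enters the FAS. Requiring the investigational product is also a defensible choice for an efficacy set, since an atezolizumab-only subject says little about the combination. All of this stands, and it limits the size of the point. It does not justify using a vaccine-based set as the only safety set. SAP 4.4.8.1 does word the AE incidence denominator as the cohort, but it presents the AE overview for the FAS, and protocol 9.9 bases safety on the FAS.

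Four stronger readings are tempting but not supported:

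- *The subject disappears from the report.* The disposition table would count the subject as treated and the listings would show the events. The loss is from the efficacy, AE and exposure summaries.
- *The exclusion can only flatter the combination.* Protocol 4.2.5.1 lets one agent continue when the other is stopped for an AE. A subject continuing atezolizumab alone could respond and still be excluded.
- *It is unclear who counts towards 14/13 and 33/35.* Protocol 9.3 and SAP 2.6.4.1 and 4.4.5.1 tie the decision counts to FAS subjects.
- *Baseline values are generally contaminated by atezolizumab.* Haematology and chemistry are drawn before each infusion (schedule footnote 8), and baseline CT and biomarker samples are taken at Screening. Mainly Visit 1 vital signs and thyroid tests remain, and their timing is not stated. With same-day dosing, Day 1 is the same under either anchor.

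Protocol Appendix 5 explains the choice of set as "to include all treated subjects for the final analysis, the FAS is now used as the primary population for all analyses". That is amendment-log text, so it serves here only as context; the mismatch lies within the current definitions.

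**Conclusion.** The mismatch is real and is in the current text of both documents. A subject given atezolizumab but no vaccine is enrolled, treated and able to have a TEAE, yet enters no AE, exposure or ORR summary. As written, the safety denominator can be incomplete.

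The consequence is probably small, because the number of such subjects is unknown and may be zero. One subject would be about 7% of a Stage 1 cohort for safety, and 1.2 percentage points of ORR at the Cohort 1 threshold (39.4% − 38.2%) if a non-responder. The direction for ORR most likely favours the combination, on the assumption that such subjects rarely respond; the documents do not make it certain. The change is worth making because the rule is best settled before data are seen in an open-label trial with continuous monitoring of responses (SAP 2.6.4).

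**What to change.** - **Safety and exposure.** Base all these summaries on every subject who received any amount of MVA-BN-CV301, FPV-CV301 or atezolizumab. Either redefine the FAS this way in protocol 9.3 and SAP 4.2, or add a safety set with this definition.
- **Primary ORR.** Preferably use the same all-treated set, counting such subjects as non-responders unless they respond. If the efficacy FAS stays vaccine-based, state why and report ORR on all treated subjects as a sensitivity analysis.
- **Time anchors.** Start Trial Day, baseline and Screening Phase at the first dose of any trial product, to match TEAE, PFS and OS. Align the SAP passages that end the pre-treatment AE period at first vaccination (Medical History definition, 4.4.8.4) with those that end it at first trial product (4.3.4, 4.4.7.6, 4.4.8.1).

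The drafting cost is a few sentences. The statistical cost arises only if such a subject occurs and the all-treated set is used for the primary test: with one non-responder within the 33, Cohort 1 power drops from 0.703 to 0.657 or 0.644, depending on stage, and type I error falls as well. Adding only a safety set leaves the primary test untouched.

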### 9.3 Analysis Populations

For the purpose of statistical analysis, there will be 2 analysis populations: Full Analysis Set (FAS) and the Efficacy Evaluable Set (EE).

The FAS consists of all subjects taking any amount of trial vaccine, whether MVA-BN-CV301 or FPV-CV301. The FAS will be the primary population for all analyses.

The EE Set consists of all subjects from the FAS who received 2 prime doses of MVA-BN-CV301 (Weeks 1 and 4).

The EE population will be used in sensitivity analyses for efficacy.

Subjects who failed to meet the EE Set criteria will be replaced unless 4 or more responses in Cohort 1 (or 3 or more responses in Cohort 2) have been observed for the FAS population, or the number of responders will still be less than 4 in Cohort 1 (or 3 in Cohort 2) even if all replacement subjects would be responders. If there are more than 14 evaluable subjects in Cohort 1 (or 13 in Cohort 2) at the end of Stage 1 analysis, or more than 33 in Cohort 1 (or 35 in Cohort 2) evaluable subjects at the end of Stage 2 analysis, primary evaluation will be based on the first 14 (or 13) accrued or first 33 (or 35) accrued FAS subjects.

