4.4.8 Safety Variables and Analyses34

4.4.8.1 Adverse Events34

4.4.8.2 Clinical Laboratory Assessments37

4.4.8.3 Vital Signs and ECG38

4.4.8.4 Physical examination39

4.5 Alterations to the Clinical Trial Protocol39

5 References40

Abbreviations

Abbreviation	Definition
AE	Adverse Event
AESI	Adverse Event of Special Interest
ADR	Adverse Drug Reaction
ALT	Alanine Aminotransferase
AST	Aspartate Aminotransferase
ATC	Anatomic-Therapeutic-Chemical
β-HCG	Beta-Human Chorionic Gonadotropin
BMI	Body Mass Index
CDISC	Clinical Data Interchange Standards Consortium
CI	Confidence Interval
CR	Complete Response
CRF	Case Report Form
CRO	Contract Research Organization
CTCAE	Common Terminology Criteria for Adverse Events, version 5.0
ECG	Electrocardiogram
eCRF	Electronic Case Report Form
EE	Efficacy Evaluable
EOT	End of Treatment
FAS	Full Analysis Set
FPV	Fowlpox Virus
FU	Follow Up
ICF	Informed Consent Form
ICH	International Conference on Harmonisation (now International Council for Harmonisation)
IMAE	Immune Mediated Adverse Event
LTFU	Long Term Follow Up
MCHC	Mean Corpuscular Hemoglobin Concentration
MCV	Mean Erythrocyte Corpuscular Volume
MedDRA	Medical Dictionary for Regulatory Activities
MMR	Mismatch Repair
MSI	Microsatellite Instability
MVA-BN	Modified Vaccinia Ankara – Bavarian Nordic
NCI	National Cancer Institute
OR	Objective Response
ORR	Objective Response Rate
OS	Overall Survival
PD	Progressive Disease
PFS	Progression Free Survival
PR	Partial Response
PT	Preferred Term
RBC	Red Blood Cell/Erythrocyte
SAE	Serious Adverse Event
SAP	Statistical Analysis Plan
SC	Subcutaneous
SD	Stable Disease

Abbreviation	Definition
SD	Standard Deviation
SOC	System Organ Class
SOP	Standard Operating Procedure
TEAE	Treatment Emergent Adverse Event
TPS	Tumor Proportion Score
UC	Urothelial Cancer
WBC	White Blood Cell/Leukocyte
WHO DDE	World Health Organization Drug Dictionary Enhanced

General Definitions

Vaccination

A vaccination in this trial means receiving subcutaneous (SC) injection(s) with either MVA-BN-CV301 or FPV-CV301.

Trial Treatment

Trial treatment refers to dosing with any of the following trial products:

- Prime with MVA-BN-CV301 given SC on Days 1 and 22.
- Boost with FPV-CV301, given SC every 21 days for 4 doses, followed by boosts every 6 weeks until 6 months on trial, then every 12 weeks until completion of 2 years.
- Atezolizumab fixed dose of 1200 mg intravenous on Day 1 of each 21-day cycle.

Trial Medication

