2.6.2 Secondary Efficacy Endpoints

- OS, defined as the time from start of treatment to the time of death from any cause.
- Duration of response, defined as the time from the initial occurrence of documented OR until documented disease progression or death due to any cause on trial, whichever occurs first.
- PFS defined as the time from start of treatment to the first event of death or progressive disease (PD) per RECIST v1.1.
- Percentage of subjects with OS and PFS at 6 (PFS only), 9 (PFS only), 12, 18 and 24 months.
- Immune-related Response Criteria assessment of response rate per iRECIST, delayed responses (pseudo-progressions), duration of response and PFS.

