4.4.5.2 Secondary Endpoints

4.4.5.2.1 Progression-Free Survival

PFS is defined as the time interval from first treatment to objective tumor progression or death. Accordingly, the precise definition of progression and the timing of CT scans to document progression are very important. Every effort must be made to assure that timeframes for post-treatment CT scans are achieved, so that both treatment groups can be usefully compared.

Assessments must be adequate to evaluate target lesions, non-target lesions, and to search for new lesions.

The secondary endpoint of PFS will be based on the investigator's assessment using RECIST v1.1 response guidelines. PFS will be defined as the time from the day of first treatment to the start of disease progression or death (any cause), whichever occurs first. Subjects who do not have disease progression or have not died will be censored at the date when the last tumor assessment determines a lack of progression. If a subject begins a new anti-cancer therapy or has radiotherapy or surgery at a lesion site prior to documented progression (or death), the subject will be censored at the last assessment where the subject was documented as progression free prior to the intervention.

The Kaplan-Meier curve for PFS and the median PFS will be presented for the FAS.

Additionally, an investigator assessed PFS analysis that includes both investigator-judged PD according to RECIST v1.1 and symptomatic deterioration will be provided.

A binary endpoint for PFS will also be analyzed at milestone time points. The number and percentage of subjects who are progression free based on the above definition at 6, 9, 12, 18, and 24 months will be summarized within the FAS. The two-sided 90% exact binomial confidence interval for the PFS at each time point will be calculated using the Clopper-Pearson method.

A recently published meta-analysis concluded that in checkpoint inhibitor trials 6-month PFS rate is recommended as an endpoint because it is the best predictor of 12-month OS rate. In the absence of prospective validation, the decision adopted is to retain 6-month PFS rate as a secondary endpoint with the aim of complement the primary endpoint ORR in the interpretation of trial results as a whole.

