4.4.5.2.2 Overall Survival

OS is defined as the time between the date of first treatment and the date of death due to any cause. Subjects who are alive or have the competing events of "definite" loss to follow-up or withdrawal of consent will be right censored at the date of last contact.

OS = Date of death/competing event/censoring - date of first treatment + 1.

Imputation of missing date parts will follow the rules previously specified. Competing events for death are “definite” lost to follow-up and withdrawal of consent for continued vital status assessments. Both competing events are subject to revision for an individual subject with the passage of time. Subjects will be censored for competing events as well as survival by using their last contact date in the clinical database.

The 12-month OS rate and the product-limit estimate of median survival, as well as their 90% confidence intervals will be summarized. A Kaplan-Meier curve will summarize OS graphically. The 18-month and 24-month survival rates will also be provided along with their 90% CIs.

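### The EE repeat of PFS and OS requires the Week 4 prime dose but starts the clock at first treatment, so each FAS death before that dose raises the EE survival curves relative to the FAS

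*SAP*

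**What the plan says.** SAP 4.2 makes the FAS the lead population: "The FAS will be the primary population for all analyses". It then gives the EE set its role: "The EE set will be used for sensitivity analyses of the primary and secondary efficacy endpoints". Protocol 9.3 is to the same effect but less specific: "The EE population will be used in sensitivity analyses for efficacy". SAP 2.6.2 counts OS, PFS, duration of response and the milestone OS and PFS percentages among the secondary efficacy endpoints, so all of them fall under that sentence.

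The first EE criterion in SAP 4.2 is "Received 2 prime doses of MVA-BN-CV301 (Weeks 1 and 4"; the second is a baseline scan assessable by RECIST. The SAP's definition of trial treatment sets the dosing days: "Prime with MVA-BN-CV301 given SC on Days 1 and 22". Table 1 in SAP 4.3.1 allows Day 18 to 26 for the Week 4 visit.

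Both clocks start earlier. SAP 4.4.5.2.1: "PFS will be defined as the time from the day of first treatment to the start of disease progression or death (any cause". SAP 4.4.5.2.2: "OS is defined as the time between the date of first treatment and the date of death due to any cause". Neither section gives a landmark, delayed entry or a separate origin for the EE set. The PFS and duration-of-response sections name the FAS, and no EE version of any survival analysis is described beyond the sentence in SAP 4.2.

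**The concern.** Whether a subject belongs to the EE set is settled about three weeks after the survival clock starts. To qualify, the subject must be alive at the second prime. Those three weeks are counted as follow-up in the EE analysis although no death could occur in them. This is immortal time created by conditioning on a later event.

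A sensitivity analysis on a subset is read as evidence on whether the FAS result is robust. Here part of any EE advantage comes from the definition of the set and not from receiving both primes. The trial has no control arm, so its survival results are likely to be set beside published results. An EE curve that leaves out deaths before dose 2 but counts from dose 1 is not on the same footing as a curve for all treated subjects.

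**Working it through.** **Plan's own figures.** The documents give no figure for EE survival. Their checkable design figures are the ORR operating characteristics in SAP 4.1. An exact two-stage binomial calculation reproduces them: Cohort 1 type I error 0.0244 and power 0.7027, Cohort 2 type I error 0.0249 and power 0.7092. They are not in dispute here.

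**Inputs**
- Time from first treatment to dose 2: Day 22 is 21 days after Day 1, so t0 = 21/30.4375 = 0.690 months. The visit window gives 17 to 25 days.
- Cohort 2 setting, Protocol 2.1 (Phase 3 trial of atezolizumab after platinum): median OS 8.6 months, 12-month OS 39.2%.
- Cohort 1 setting, Protocol 2.1 (single-arm Phase 2 trial in cisplatin-ineligible patients): median OS 15.9 months, 12-month OS 75%.
- Maximum cohort sizes, SAP 4.1: 33 and 35.
- Assumption, not in the documents: exponential survival, S(t) = 0.5^(t/median), with everyone alive at t0 receiving dose 2.

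**Formulae.** Share dying before dose 2 = 1 − S(t0). With the clock at dose 1, S_EE(t) = S(t)/S(t0) for t ≥ t0. Setting this to one half gives EE median = median + t0.

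**Cohort 2, matched to the median.** S(t0) = 0.5^(0.690/8.6) = 0.946, so 5.4% die before dose 2 (4.4% to 6.4% over the window), or 35 × 0.054 = 1.9 subjects. S(12) = 0.5^(12/8.6) = 0.380; EE 0.380/0.946 = 0.402 (0.398 to 0.406 over the window). Median 8.6 + 0.69 = 9.3 months.

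**Cohort 1, matched to the median.** S(t0) = 0.5^(0.690/15.9) = 0.970, so 3.0% die (2.4% to 3.5%), about 1.0 of 33. S(12) = 0.593; EE 0.593/0.970 = 0.611. Median 15.9 + 0.69 = 16.6 months.

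**Cohort 1, matched to 12-month OS.** S(t0) = 0.75^(0.690/12) = 0.9836, so 1.6% die, about 0.5 of 33. EE 12-month OS = 0.75/0.9836 = 0.7625. The two Cohort 1 versions differ because one exponential curve cannot fit both published figures: a 15.9-month median implies 59.3% at 12 months, not 75%.

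**Check without a survival model, Cohort 2.** Suppose 14 of 35 are alive at 12 months (40.0%). Removing 1, 2 or 3 deaths before dose 2 gives 14/34 = 41.2%, 14/33 = 42.4% or 14/32 = 43.8%.

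**Deterioration.** If 25% to 50% of those who die between Day 22 and month 3 also miss dose 2 (an assumed share), simulation gives a rise in 12-month OS of about 4 to 6 points in Cohort 2 and 3 to 5 points in Cohort 1.

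**After restarting the clock at dose 2.** Under the same constant hazard the EE medians return to 8.6 and 15.9 months.

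**The case against.** **Reach.** A reader might infer that the trial's survival results are overstated. The documents do not support that. The FAS is primary throughout, the PFS section ties its curve, median and milestone rates to the FAS, and PFS and OS carry no hypothesis test or stopping rule. Only the EE repeat is affected, and it rests on one sentence in SAP 4.2. This stands and sets the scope of the point.

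**Direction.** A reader might also infer that the EE analysis can only look better than the FAS. That is wrong. The EE set also drops subjects without an assessable baseline scan. Protocol 4.2.5.1 allows one agent to continue when the other is stopped for an adverse event, so a subject who missed the second prime may still survive long. From 14/35 (40.0%), dropping one early death and one 12-month survivor gives 13/33 (39.4%). Only the early-death component has a certain direction.

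**PFS.** The first scheduled scan is at about Week 10 (SAP 2.6.4.1), so few progressions can be documented before Day 22. For PFS the artefact comes mainly from deaths and unscheduled progression.

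**Size.** The life-expectancy criterion of at least 12 weeks, and ECOG below 2 in Cohort 2, may make deaths in the first three weeks rarer than an exponential curve implies. One could build a larger figure by supposing that 10% miss the second prime and all die within the year (0.392/0.90 = 43.6%), but the documents support neither part. A shift of 2 points is also small beside a 90% interval half-width of roughly 1.645 × √(0.4 × 0.6/35) = 0.136, about 14 points. That comparison helps only in part: the EE set is a subset of the FAS, and the sensitivity analysis is read for the difference between the two.

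**Remedy.** A landmark gives the EE analysis a different origin from the FAS and still selects subjects fit for dose 2. Both points are correct, and the labelling in the fix addresses them.

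**Conclusion.** The point holds for the EE sensitivity analyses of PFS and OS, and for nothing else. As written, these analyses contain guaranteed survival up to dose 2, and every FAS death before dose 2 raises the EE curve relative to the FAS. That follows from the definitions alone.

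Its size does depend on assumptions. Under exponential survival with the protocol's reference figures, the gain in 12-month OS is about 2 points in the Cohort 2 setting and about 1 to 2 points in the Cohort 1 setting. Where the model is matched to the median, the median gains about 0.7 months. The gain is zero if nobody dies before dose 2, may be smaller because of the life-expectancy criterion, and is larger if deteriorating subjects miss dose 2. The net EE-minus-FAS difference has no guaranteed sign, because the other exclusions can act either way. Duration of response starts at response and does not share this problem.

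This is a modest flaw in an analysis that decides nothing, but it is cheap to remove before the EE results are read as support for the FAS.

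**What to change.** In SAP 4.2, adopt one of two wordings:

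1. Limit the EE set to ORR and leave PFS and OS on the FAS only.
2. Keep EE PFS and OS, but time them from the date of the second prime dose as a landmark analysis. Label them as conditional on receiving both primes and as not directly comparable with FAS survival from first treatment.

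Under either option, show the outcomes of the FAS subjects excluded from the EE set beside the exclusion reasons. SAP 4.4.7.2 already plans to report the reasons; the outcomes are the addition.

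The cost is a change of SAP wording and, under option 2, one changed start date. No new data are needed. EE survival figures would become slightly less favourable. Option 2 removes the artefact from deaths before dose 2, but not the selection of subjects fit to receive that dose, and its time origin differs from that of the FAS.
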